- ** From D366 to D731, UK reconsented participants' parents/LARs are requested to capture in a memory aid any hospitalizations and emergency-room visits experienced by the participants. The memory aid will be reviewed by the investigator or site staff during the 18-month and 24 month follow-up calls to collect any information on SAE or LRTI hospitalizations that may have occurred since the previous contact. If an SAE is reported, the investigator or site staff will assess the relationship and only related SAE will be reported in the eCRF.
- †† Immediate AE occurring within 30 minutes after immunization will be collected on V01.
- Assessment of LRTI (inpatient) requiring hospitalization. In case of hospitalization due to LRTI symptoms at any time during the study after randomization, an RSV test is to be performed as per the hospital routine practice. Test results and information about the LRTI hospitalization such as O2 saturation, respiratory rate, oxygen supplementation, intravenous fluid administration, admission to intensive care unit, date of admission and of discharge are to be collected retrospectively.
 - It is to be noted that, for participants hospitalized due to LRTI symptoms whose participation in the study is prematurely terminated, the Investigator or designee may seek information on the LRTI hospitalization for the assessment of efficacy endpoints. This retrospective collection of information on LRTI hospitalization for participants withdrawn from the study will be possible only if the parents or LARs provided consent by ticking the corresponding box in the informed consent form.
- A safety follow-up phone contact is to be made at 12 months post-dosing/randomization. For participants who have prematurely terminated the study (eg, no answer to monthly electronic contact within the first 6 months post-dosing/randomization), the site or authorized designee should attempt to contact them and complete this 12-month safety follow-up to identify the occurrence of any SAEs, MAAEs, and AESIs that had not yet been reported, except if they specified that they do not want to be contacted again and it is documented in the source document.

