- *** Be certain to record concomitant medications at the time of dosing/randomization, including vaccine administered in the 14 days prior to Visit 01, during Visit 01, and up to 14 days after Visit 01. Concomitant reportable medications will be collected in the event of an AE (including an LRTI hospitalization) through a phone contact by the medical call center or through the participant's medical records, as applicable. Sites will also be asked to report any routine immunization with nirsevimab (Beyfortus®). See Section 6.8 for details on concomitant reportable medications.
- ††† Vaccine history is to be recorded in the eCRF. This includes vaccines co-administered during Visit 01, as well as vaccines administered up to 14 days before and up to 14 days after dosing/randomization.
- ‡‡‡ Immunization is only for Group 1, the nirsevimab arm. Participants randomly assigned to Group 2 will receive no RSV preventive intervention.
- Parents or LARs of the participant will be instructed to keep a study card that indicates study participation. The study card is to be presented to the hospital in the event of hospitalization due to any cause. The site or the Investigator's contact details should be reported on it.
- **** A safety follow-up phone contact is to be made at 18 months and at 24 months post-dosing/randomization for UK reconsented participants only. During these calls, the investigator or site staff will interview the participant's parents/LARs to review the memory aid and collect any information on SAE or LRTI hospitalizations that may have occurred since the previous contact. If an SAE is reported, the investigator or site staff will assess the relationship and only related SAE will be reported in the eCRF.
- †††† Consent of the Addendum to Informed Consent Form can be obtained from parents/LARS at any time prior or after the D366 phone call (up to D731). An electronic ICF process or consent by email can be implemented if applicable as per country regulations. Following the D366 phone call, an on-site visit can be organized for participants' parents/LARs unable to realize the e-consent or email consent in order to collect the paper consent.
- ‡‡‡‡ Only concomitant medication related to related SAE and/or LRTI hospitalization will be collected. Sites will also be asked to report any routine immunization with nirsevimab (Beyfortus).

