At the time of Second Year Analysis, incidence of RSV and all-cause LRTI hospitalization in UK reconsented participants only from 366 days post-dosing/randomization to 731 days post-dosing/randomization will be summarized by the treatment group. Descriptive statistics will be provided only.

Above analyses will be performed only in participants without the studied event before Day 366. In addition, number and percentage of participants with above events before and after Day 366 will be provided.

For UK reconsented participants who completed the study, the end date of the follow-up time will be the end of study date or the last available date with confirmation of no RSV/all-cause LRTI hospitalizations, whichever is earlier.

For UK reconsented participants who had contact for safety events after reconsented and discontinued from the study before Day 731, the end date of the follow-up time will be the last available date with confirmation of no RSV/all-cause LRTI hospitalizations.

For UK reconsented participants who had no contact for safety events at all after reconsenting, the end date of the follow-up time will be the consent date.

For UK reconsented participants who had no contact for safety events at all at the time of First Year Analysis but reported safety events with confirmation of no RSV/all-cause LRTI hospitalizations afterwards, the end date of the follow-up time will be the end of study date or last available date with confirmation of no RSV/all-cause LRTI hospitalizations, whichever is earlier.

Notes:

- If RSV/all-cause LRTI hospitalizations occur after Day 731, it will not be considered and then the end date will be Day 731.

- If a participant receives Beyfortus as part of a routine immunization, any RSV/all-cause LRTI hospitalization occurring after Beyfortus immunization but between Day 366 and Day 731 will not be considered and the end date will be the date of injection of Beyfortus.

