6.6.9.2.1. Algorithm for Follow-up Time

The start date for the follow-up will be the date of randomization for participants who are randomized to no intervention, the date of treatment dosing for participants who are randomized to nirsevimab and treated, and the date of randomization for participants who are randomized to nirsevimab but not treated.

For the participants who have the event of interest in the corresponding timeframe for the Second Year Analysis, the end date of the follow-up time will be the date of hospital admission; otherwise the participants will be censored as defined in the following:

- **From 366 Days Post-Dosing/Randomization to 511 Days Post-Dosing/Randomization**

The analysis will be performed only in participants without the studied event before Day 366.

For UK reconsented participants who completed the study, the end date of the follow-up time will be Day 511 or last available date with confirmation of no RSV/all-cause LRTI hospitalizations, whichever is earlier.

For UK reconsented participants who had contact for safety events after reconsented and discontinued from the study before Day 511, the end date of the follow-up time will be the last available date with confirmation of no RSV/all-cause LRTI hospitalizations.

For UK reconsented participants who had no contact for safety events at all after reconsenting, the end date of the follow-up time will be the reconsent date.

Notes:

- If the event of interest occurs after Day 511, it will not be considered and then the end date will be Day 511.
- If a participant receives Beyfortus as part of a routine immunization, any event occurring after Beyfortus immunization but between Day 366 and Day 511 will not be considered and the end date will be the date of injection of Beyfortus.

- **From 512 Days Post-Dosing/Randomization to 731 Days Post-Dosing/Randomization**

The analysis will be performed only in participants without the studied event before Day 512.

For UK reconsented participants who completed the study, the end date of the follow-up time will be Day 731 or last available date with confirmation of no RSV/all-cause LRTI hospitalizations, whichever is earlier.

For UK reconsented participants who had contact for safety events after reconsented and discontinued from the study, the end date of the follow-up time will be the last available date with confirmation of no RSV/all-cause LRTI hospitalizations.

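### UK extension consent stays open until Day 731 while the second-year tables take in every reconsented infant whatever the reconsent date, and the end-date rules for infants with no later contact do not agree

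*Protocol*

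**What the plan says.** Protocol 1.3, Table 1.2, footnote ††††: the extension consent "can be obtained from parents/LARS at any time prior or after the D366 phone call (up to D731". The same footnote adds: "An electronic ICF process or consent by email can be implemented if applicable as per country regulations". Footnote ** covers collection once a family has joined: "From D366 to D731, UK reconsented participants' parents/LARs are requested to capture in a memory aid any hospitalizations and emergency-room visits".

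SAP 6.6.4.3.6 defines the second-year secondary analysis. Incidence in "UK reconsented participants only from 366 days post-dosing/randomization to 731 days post-dosing/randomization will be summarized by the treatment group". The only entry condition concerns earlier events: "Above analyses will be performed only in participants without the studied event before Day 366". Nothing refers to the reconsent date, and no analysis by reconsent timing is planned.

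The end-date rule for an infant never reached again is this: "had no contact for safety events at all after reconsenting, the end date of the follow-up time will be the consent date". SAP 6.6.9.2.1 uses the same rule in its Day 366 to 511 and Day 512 to 731 windows: for those who "had no contact for safety events at all after reconsenting, the end date of the follow-up time will be the reconsent date". In its through-Day-511 and through-Day-731 windows, an infant with no contact by that day instead ends at the start date. Section 6.6.9.2.1 starts follow-up at randomization or dosing for every window.

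**The concern.** The period in which a family may join is also the period in which the outcome occurs. A family deciding at, say, Day 600 may already know whether the infant was hospitalized in the second season, and knows the arm. If willingness to join depends on both, the infants in the table are selected on outcome by arm.

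The extension exists to meet a post-marketing commitment on antibody-dependent enhancement in the second season (Protocol 10.6, Amendment 1; also Protocol 4.2). With no formal test, readers will compare the two arm incidences directly, so selection could hide or mimic a harm signal.

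The no-contact rule is a separate matter. It can present an infant as event-free over a period that no contact covered, and it does not work in every window where it is used.

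**Working it through.** The plan states no figure on this point, so there is none to reproduce. The check applies its rules and then bounds the effect under stated assumptions.

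**1. Late joining is foreseen.** Protocol 10.6 says that consent will be asked at the end of the first year, and the schedule marks it at Day 366. But the footnote runs to Day 731, and SAP 6.2 has a category for UK infants who finished the 12-month call and have not yet reconsented. Amendment 1 is dated 19 July 2023. An infant enrolled on the planned first date, 1 September 2022, reached Day 366 on 1 September 2023, about six weeks later.

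**2. How much of the season is exposed.** Assume that the second season runs from 1 October 2023 to 29 February 2024 (the protocol gives about five months, usually starting in October or November).

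| Enrolled | Second season in study days |
|---|---|
| 1 September 2022 | D396 to D547 |
| 1 December 2022 | D305 to D456 |
| 28 February 2023 (planned last) | D216 to D367 |

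For the earliest infants, reconsent after Day 547 follows the whole season. For the latest, nearly all of it falls in year 1, which is followed whatever the reconsent status.

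**3. Selection.** Let L be the share of families deciding after Day 366, 50% their base chance of joining, and k the factor by which an event changes that chance in one arm only. With rare events and equal joining by event-free families, an arm's inclusion probability for event families is q = (1 − L) + L × 0.5 × k, and the observed ratio is the true ratio × q(nirsevimab) / q(control). L and k are assumptions.

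- L = 10%, k = 2 in one arm: 1.00/0.95 = 1.05, or 0.95 if it is the other arm.
- L = 25%, k = 2: 1.00/0.875 = 1.14, or 0.875.
- L = 50%, k = 2: 1.00/0.75 = 1.33, or 0.75.
- L = 50%, k = 0.5: 0.625/0.75 = 0.83, or 1.20.

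These figures treat every event in a late-deciding family as known at the decision. If only half are, k = 2 acts as k = 1.5, and L = 50% gives 0.875/0.75 = 1.17, or 0.86.

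**4. The no-contact rule.** Days credited in the Day 366 to 731 window = reconsent day − 366. In the Day 512 to 731 window they are reconsent day − 512.

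| Reconsent day | Credited from D366 | Share of 365 days | Relative to D512 |
|---|---|---|---|
| 400 | 34 | 9% | −112 |
| 450 | 84 | 23% | −62 |
| 511 | 145 | 40% | −1 |
| 548 | 182 | 50% | 36 |
| 640 | 274 | 75% | 128 |
| 731 | 365 | 100% | 219 |

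Reconsent before Day 366, which is allowed, likewise gives an end date before the Day 366 window opens. The through-Day-511 and through-Day-731 rules credit essentially nothing, since the end date equals the start date. The conditions also differ: the first set refers to contact after reconsenting, the second to any contact by that day. An infant with first-year contact and none after reconsenting is not clearly placed in the second set.

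**5. Effect on a person-time rate.** Let g be the share who reconsent late and are never contacted, c their mean reconsent day, and 365 days the follow-up of everyone else. Unconfirmed share = g(c − 366) / [g(c − 366) + (1 − g) × 365].

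- g = 1%, c = 457: 0.91/(0.91 + 361.35) = 0.3%.
- g = 20%, c = 640: 54.8/(54.8 + 292) = 15.8%.

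A person-time rate would be lowered by the same share. If the share is equal in both arms, the ratio does not move.

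**The case against.** The strongest reply is that little rests on this. SAP 6.6.4.3.6 and 6.6.9.2 give descriptive statistics only, and SAP version 6.0 removed inference for the UK reconsented participants. That stands, and it limits the point to interpretation of the second-year tables.

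A reader might infer that all time before a late reconsent is unconfirmed. The documents do not support that. Protocol 8.1 takes second-year data from medical records, and the 18- and 24-month calls ask about LRTI hospitalizations since the previous contact, which can reach back before reconsent. For infants who complete, or who discontinue after some contact, follow-up needs a date on which absence of the event was confirmed. Unconfirmed credit arises only for families who join late and then have no safety contact.

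A reader might also take an end date before the window as a second bias. It is not: the sensible reading is no time in that window. It needs stating, because the section's start date is randomization or dosing.

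SAP 6.6.4.3.6 does not say whether incidence is per infant or per person-time. Per infant, the credited days change nothing, but the unconfirmed infant still sits in the denominator as event-free.

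Finally, starting second-year time at reconsent, or limiting the main table to early joiners, could discard record-verified hospitalizations, the events that the enhancement question needs. That argues against changing the main analysis. It does not argue against a sensitivity table.

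**Conclusion.** The point holds in two parts.

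(i) Reconsent timing: a cheap improvement. Entry can follow the outcome, and nothing planned would show whether it did. A reader might infer that the second-year comparison is biased for or against nirsevimab. The documents do not support either: they give no number of late reconsenters, so size and direction are unknown. The range 0.75 to 1.33 rests on the assumed 10% to 50% late deciders, a 50% base chance of joining, and a 0.5- to 2-fold shift in one arm; it narrows when fewer events precede the decision.

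(ii) No-contact end date: wrong as written. It credits 0 to 365 unconfirmed days per affected infant, precedes the window for reconsent before Day 366 or Day 512, and does not match the cumulative windows. The 0.3% to 15.8% share of person-time is likewise assumed.

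The primary and key secondary results are not affected. Neither is the wheeze analysis in 6.6.4.3.7, which has its own rule based on record review.

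**What to change.** (i) In SAP 6.6.4.3.6 and the 6.6.9.2 windows, keep all reconsented infants as the main descriptive table. Add a table of reconsent timing by arm, and a sensitivity analysis limited to infants reconsented by Day 366 + 14 days.

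(ii) In SAP 6.6.4.3.6 and 6.6.9.2.1, replace the no-contact rule. An infant with neither contact nor record confirmation after reconsenting contributes no time to, and is not in the denominator of, the windows starting at Day 366 or Day 512. State that time in those windows counts from the window's first day, and word the no-contact condition the same way in the cumulative windows.

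Cost: SAP wording, one extra table, and slightly fewer infants or less person-time. The reconsent date is already used in the SAP, so no new data collection is needed.

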2.1 Study Rationale

Respiratory syncytial virus (RSV) is a common respiratory pathogen that causes disease throughout life but particularly in the early years. It is the most common cause of acute respiratory illness in infants and is associated with significant morbidity and mortality.

Currently, the only licensed preventive measure against RSV is palivizumab, a monoclonal antibody licensed for use in a small subset of the pediatric population. Although it depends on guidelines from recommending bodies in individual countries, the eligible pediatric population usually includes infants born at ≤ 35 weeks gestational age and up to 6 months of age at the start of the RSV season, and those with chronic lung disease and congenital heart disease up to 24 months of age^a. Overall, the group of eligible infants represents 2-6% of the birth cohort annually depending on each country's guidelines (1) (2) (3). In the population of infants who do not qualify for palivizumab administration, the standard of care does not include any preventive measure and is limited to supportive care in the event of RSV infection.

Nirsevimab is a recombinant human immunoglobulin G1 kappa monoclonal antibody that neutralizes RSV by binding to a highly conserved, neutralizing epitope on the prefusion conformation of the RSV F protein. This binding prevents the RSV F protein from mediating fusion between the viral and cellular membranes, which is an essential step for viral entry.

The primary objective of the clinical development program for licensure was to demonstrate that nirsevimab will protect preterm and term infants from medically-attended lower respiratory tract infection (LRTI) caused by RT-PCR confirmed RSV during their first RSV season as measured by a significant reduction in disease incidence.

The Phase IIb pivotal study conducted in healthy preterm infants born at ≥ 29 to < 35 weeks gestational age included a secondary endpoint specifying RSV-confirmed hospitalizations (4). Based on a similar study design, a Phase III study (MELODY) was conducted in healthy late preterm and term infants ≥ 35 weeks gestational age. It also included RSV hospitalizations as a secondary endpoint. In both studies, RSV hospitalizations was defined as the subset of cases

Recommendations from the British Joint Committee on Vaccination and Immunisation: https://www.nitag-resource.org/sites/default/files/ddf283f66b77b34a6821e8d6f000947b74f6b68b_1.pdf;
Recommendations from the German Arbeitsgemeinschaft der Wissenschaftlichen Medizinischen Fachgesellschaften: https://www.awmf.org/uploads/tx_szleitlinien/048-0121_S2k_Prophylaxe-von-schweren_RSV-Erkrankungen-Risikokindern-Palivizumab 2018-11.pdf

^a Recommendations from the French Haute Autorité de Santé: https://www.has-sante.fr/jcms/c_2756580/fr/synagis-palivizumab;

meeting the criteria for the primary endpoint (ie, medically-attended RSV LRTI) that were also hospitalized.

During the planning of the MELODY study, it was recognized that the management of more serious RSV disease had been shifting to the outpatient setting (see Section 7b of FDA 2017) and that the incidence of RSV hospitalization in late preterm and term infants may be too low for the secondary endpoint to reach statistical significance within MELODY alone. This effect was compounded by the reduction in virus circulation and healthcare attendance as a result of public health measures taken during the COVID-19 pandemic, resulting in a much smaller number of hospitalizations.

The decision to hospitalize an infant with respiratory illness is made upon the judgment of the attending physician, but these decisions are underpinned by national guidelines that determine sets of criteria that, when met, indicate illness requiring secondary care input. These guidelines are broadly similar internationally and include signs of increased respiratory effort (tachypnea > 50 breaths/minute, moderate or severe retractions), compromised oral intake or hypoxia, all of which are associated with very severe illness. Many guidelines set the threshold for hypoxia at 90-92% oxygen saturation and this is widely accepted as an indicator of severe enough disease to require hospitalization. However, the decision to hospitalize is not contingent only on evident hypoxia as the presence of above-mentioned signs are also accepted as indicators of very severe disease (5).

The hospitalization of an infant with RSV constitutes a significant individual, family, and healthcare burden (6). Preventing serious deterioration in clinical condition due to RSV infection to the point of requiring hospitalization —a widely accepted indicator of disease severity— is one of the primary aims of the management and prevention of RSV in infants. The impact of nirsevimab on hospitalization of infants with RSV and its inclusion in the approval process is of key importance to physicians, for use in their clinical decision making, and parents/LARs alike. Hospitalization of infant due to RSV LRTI does have some far-reaching consequences as as many as one-third of all children who are hospitalized due to RSV are unnecessarily treated with antibiotics (7), even though routine antibiotic therapy for bronchiolitis is discouraged (8) (9). The unnecessary use of antibiotics is associated with short term adverse events (gastrointestinal complaints, diarrhea, exanthema), increased selective pressure on resistant bacteria, and it displays an adverse impact on the composition of the infant's microbiome (10).

The nirsevimab clinical development program has demonstrated the safety profile of the product, supporting investigation in a larger population, and delivered convincing efficacy results in both preterm and term infant populations, supporting its use in all infants.

In this context, an investigation of the prevention of hospitalization^a and of very severe disease due to RSV is planned for healthy late preterm and term infants, under conditions as similar as possible to the real world.

_

^a "Hospitalization" is defined as the decision to admit to in-patient care by the treating physician.

